1  
2

**Brief Title:** FrAilty Care and wEll-funcTion in  
Community Dwelling Older Adults  
(FACET)

**Official Title:** Effect of Online Support and Patient  
Empowerment on Functional Ability and  
Well-being in Older Adults: a Pilot Study

3

4 Date of document: 28-3-2018

5

6 Uploaded to Clinicaltrials.gov: 19-9-2018

7

8   **Method**

9   *Participants*

10   Forty older adults (n-female: 6, n-male: 10, age: xx years, height: xx m, mass: xx kg), residing in the  
11   community and recruited via convenience sampling, participated in the study. Participants were  
12   excluded if they had moderate/severe dementia at baseline (defined as Mini Mental State  
13   Examination < 23), severe, disabling stroke at baseline within the previous 6 months (defined as new  
14   or previous stroke with Barthel Index < 9), or a recent (< 3 months prior randomisation) myocardial  
15   infarction, or unstable angina. In addition, participants were excluded if they were currently  
16   undergoing treatment that includes exercise and diet advice by health professionals and were referred  
17   at discharge for condition-specific rehabilitation (e.g. pulmonary rehabilitation, stroke rehabilitation)  
18   within the previous 6 months. The study received ethical approval from the University ethics  
19   committee and all participants were made aware of the nature of the study and their right to withdraw  
20   at any time, before providing written informed consent. All aspects of the study were conducted in  
21   accordance with the Declaration of Helsinki.

22

23   *Procedures*

24   The trial used a parallel-group design with four intervention arms in a two-by-two factorial design.  
25   Arms were based on the factors of 'consultation type' and 'intervention support' and consisted of  
26   professional led consultation with online support (PLOS), professional led consultation without online  
27   support (PLNS), participant empowered consultation with online support (PEOS) and participant  
28   empowered consultation without online support (PENS). Participants were randomly allocated to a  
29   group based on minimization for frailty status, age and gender.

30

31   Participants attended 2 visits prior to the intervention and 1 visits following the intervention. Various  
32   functional ability assessments and health related questionnaires were completed prior to the trial  
33   during visit 1 and 2 and repeated after 12-14 weeks during visit 3. During the second visit, participants  
34   received a consultation with advice on making lifestyle changes to promote healthy ageing. Between  
35   the first visit and second visit and a week before the third visit, participants collected 3 morning void  
36   urine samples at home for the determination of their nutritional status.

37   For PLOS and PLNS, the consultation was led by the professional and lifestyle recommendations were  
38   based on ViviFrail recommendations and personal experience. In contrast, during PEOS and PENS, the  
39   consultation was led by the participant, and started with the questions 'What matters to you', and  
40   'What are your goals'. The professional based the lifestyle recommendations based on these  
41   responses.

42   For PLOS and PEOS, the 12-week intervention included access to an online monitoring platform. The  
43   online platform provided the lifestyle recommendations and consisted of a diary of activities,  
44   examples of exercises, general advice and instructions for monitoring and self-assessment. For PLNS  
45   and PENS, there was no access to the online monitoring platform, and lifestyle recommendations were  
46   provided on paper to the participant.

47   The consultation was based on the physical ability assessment, risk of falling, and completed  
48   questionnaires. Behaviour change advice as part of the lifestyle recommendations were derived from  
49   the COM-B model, which assumes that behaviour (B) is determined by capability (C), Opportunity (O)

50 and motivation (M). The capability was offered as feedback from the physical ability assessment and  
51 the motivation was assessed with the 'stages of change ladder'. The opportunities were in the form  
52 of personalized and individually tailored recommendations. Altogether, SMART goal setting and  
53 implementation intentions formed the methods of the lifestyle recommendations. The lifestyle  
54 recommendations made were recorded and included characteristics of type of exercises included  
55 (balance, strength, flexibility, multi-component, equipment used, nutrition, physical activity tasks),  
56 identified goals and action plans (frequency, duration, etc.).

57 Functional ability assessments performed prior and following the intervention consisted of the Short  
58 Physical Performance Battery (SPPB), timed-up-and-go (TUG), grip strength, usual walking speed, the  
59 6 Minute Walk Test (6MWT), the semantic fluency test and body composition analysis. The SPPB  
60 consists of a scoring system based on the ability to complete 10 seconds of narrow, semi-tandem and  
61 tandem stance position while standing upright, the time taken to complete 5 chair rises at maximum  
62 speed, and usual walking speed. The TUG consists of the time taken using an accelerometer (G-Walk)  
63 to get up from a chair, walk around a cone 3 meters away and return to sit down and is performed at  
64 the participant's usual and comfortable speed. Grip strength was assessed as the maximal value  
65 obtained from three attempts with each hand using a dynamometer (Takei). Usual walking speed was  
66 determined over a distance of 8 meters, with timing gates placed 4 meters interspaced in the middle  
67 of the path. Spatio-temporal variables were derived from an accelerometer (G-walk) and consisted of  
68 stance duration, swing phase duration, step length and propulsion of right and left leg. The 6MWT  
69 consists of walking the further distance possible in 6 minutes around 2 cones places 10 meters apart.  
70 The SFT consists of the ability to mention as many words starting with a particular letter in one minute.  
71 Body composition analysis and bone mineral density assessment of the hip and spine was performed  
72 using whole-body DXA scanning (Hologic) to determine appendicular lean mass and body fat  
73 percentage, and body impedance analysis (BodyStat) to determine hydration status.

74 Health related questionnaires consisted of the Lawton-Brody and Barthel index to assess the level of  
75 abilities performed during daily living. Frailty was assessed using the FRAIL scale, the Frailty Trait scale  
76 and the frailty phenotype model. The frailty phenotype evaluation was derived from the usual walking  
77 speed, grip strength, a physical activity questionnaire and two questions related to the presence of  
78 unintentional weight loss and exhaustion. Physical activity levels were assessed with the CHAMPS.  
79 Well-being and quality of life were assessed with the WEMWBS, the SF-36 and EuroEQ-5d5L.  
80 Healthcare Resource Use was assessed during the 12-week intervention.

81 Nutritional status was assessed based on urine metabolomics, the Mini-Nutritional Assessment, the  
82 SNAQ and diet quality assessment. Urine was collected at home, using validated urine collection  
83 techniques to store and transport urine samples. Urine was collected at the 2nd and 3rd visit and stored  
84 in -80° until further analysis. Dried blood spot samples were collected at home using a Whatman  
85 Protein Saver Card to determine lipid levels. During the first visit, a finger prick blood spot sample was  
86 to determine Hba1C levels as an indicator of diabetes status, and assess LDL, HDL and total cholesterol.

87

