#### 88 *Data analysis*

89 All scores are standard derived from the tests itself, and data analyses processes have been published  
90 previously. Standard Operating Procedures are available upon request.

91 Statistical Analysis

92 Evaluation of the pilot consisted of the number of participants refusing to be allocated to their original  
93 group. If refused, participants were offered the alternative group ('cross-over'), but excluded from  
94 statistical analysis. Intervention recruitment, adherence (online platform usage, self-monitoring  
95 frequency, usage of support materials provided) and retention were considered sufficient if:

- 96 - with 3 participants per week (and relative to those screened, the consent rate taken into  
97 account),  
98 - adherence to the intervention program exceeding 70% and  
99 - 95% retained at follow up, respectively.

100 The lifestyle recommendations made were recorded for subsequent qualitative analyses and  
101 quantification of type of exercises included (balance, strength, flexibility, multi-component,  
102 equipment used, nutrition, physical activity tasks) as part of the pilot study evaluation.

103 Adverse event occurrence will be recorded. Protocol evaluation will consider time needed for the  
104 assessment and questionnaires and the consultation, support time needed for online monitoring and  
105 engagement during the intervention, to enable appropriate costing for future trials and revise  
106 accordingly. Participant characteristics (frailty, disability) will be summarized to determine future  
107 recruitment criteria.

108 Estimated sample size and confidence intervals will be initially based on primary outcome measures:  
109 Well-being (WEMWBS), Grip strength, Walking speed and SPPB. From those, but possible the  
110 secondary outcome measures, a primary outcome variable would be determined for the future  
111 randomized control trial.

112 Secondary outcome measures consist of:

- 113 - Functional ability performance, including timed-up-and-go, chair-stand test, balance,  
114 flexibility, 6MWT.  
115 - Dietary analyses  
116 - Healthcare Resource Use (i.e. hospital visits, GP appointments) assessed using a Healthcare  
117 Resource Use questionnaire at baseline and 12 weeks, to assess potential follow up impact  
118 due to inadvertent worrying of participants.  
119 - Qualitative feedback from assessors and participants about FACET  

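### Does a sex breakdown that sums to 16 undermine the stated sample of forty?

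*Combined protocol and SAP*

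**What the plan says.** Line 10, under Participants in the Method section, reads "Forty older adults (n-female: 6, n-male: 10, age: xx years". The bracket goes on with "height: xx m, mass: xx kg", so three of its five entries are blank. The sentence ends in the past tense: the forty were "community and recruited via convenience sampling, participated in the study".

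The Procedures section describes "four intervention arms in a two-by-two factorial design", with allocation to a "group based on minimization for frailty status, age and gender". It gives no number per arm.

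The Statistical Analysis section sets three feasibility criteria: a recruitment rate of 3 per week, adherence above 70%, and "95% retained at follow up, respectively". On refusals of allocation it says: "If refused, participants were offered the alternative group ('cross-over'), but excluded from" the statistical analysis. It states no alpha, power, effect size or standard deviation for this pilot. Its sample-size sentence concerns the future trial.

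**The concern.** A total and its breakdown, given in one sentence, ought to agree. Here they differ by 24 people, and the document has no second total, participant flow or per-arm count to settle which is right. The past tense makes it harder to read forty simply as a target.

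Two uses of the number could suffer. The retention criterion is a percentage, so the losses it tolerates depend on the denominator. The estimates meant to size the next trial also become less precise as the sample shrinks. If the true number were 16, the pilot would be much weaker than a reader of line 10 would think.

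A related doubt is whether people who refuse their allocation count in the retention denominator.

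**Working it through.** **Inputs.** From line 10: total 40, women 6, men 10. From Procedures: four arms. From Statistical Analysis: retention 95%, recruitment 3 per week.

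**The sum.** 6 + 10 = 16. 40 − 16 = 24, and 24/40 = 60%. The stated total is not reproduced.

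**Could the counts mean something else?**
- Per arm: 4 × 16 = 64.
- Per factor level: 2 × 16 = 32.
- One count mistyped: 40 − 6 = 34 men, or 40 − 10 = 30 women.

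Neither multiple gives 40, and nothing in the text supports a particular typing error. The rate of 3 per week has no recruitment period attached, so no total can be derived from it.

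**Is sex missing for 24 people?** Minimisation on gender requires each person's gender at allocation. The most that can be said is that line 10 does not report it for 24 of the forty.

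**What the retention rule would allow.** The text does not say whether it means at least 95% or more than 95%. The last two columns give the chance of meeting the rule if each participant's true retention probability is 0.95 (an assumption), from the binomial distribution.

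| Denominator | Losses allowed, at least 95% | Losses allowed, more than 95% | Chance, at least 95% | Chance, more than 95% |
|---|---|---|---|---|
| 40 | 2 (38/40 = 95.0%) | 1 | 0.677 | 0.399 |
| 39 (one refuser removed) | 1 (37/39 = 94.9% fails) | 1 | 0.413 | 0.413 |
| 16 | 0 (15/16 = 93.75% fails) | 0 | 0.440 | 0.440 |

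For 40 under the strict reading: 0.95^40 + 40 × 0.05 × 0.95^39 = 0.399. The apparent fall from 0.68 to 0.41 when one person is removed arises only because 38/40 is exactly 95%. Under the strict reading it disappears.

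**Precision.** The half-width of a main-effect 95% interval, in SD units, is t(0.975, df) × √(2/n per side). This assumes equal allocation, no losses and a four-cell residual.
- 20 against 20, 36 df: 0.64 SD.
- 8 against 8, 12 df: 1.09 SD.

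The second figure applies only if 16 is the true study size, which no passage states.

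**Where the sex counts are used.** None of the three feasibility criteria refers to them. The participant characteristics named for summary are frailty and disability. The sample-size sentence rests on well-being, grip strength, walking speed and SPPB. Minimisation uses each person's gender, not the totals in line 10.

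**The case for a change.** The best case for acting is that forty is the document's only sample-size figure and its own sentence contradicts it. The blank entries are visibly blank, whereas 6 and 10 read as real counts, and the forty are said to have taken part. An unfinished template is therefore an explanation and not a reconciliation. A text correction would also cost almost nothing.

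That stands as an observation. The arithmetic is wrong as printed, and the documents cannot show which figure is in error. But they do lean one way. Besides the blank entries, the Statistical Analysis section speaks of adverse events and participant characteristics in the future tense, which fits a manuscript-style draft written before participant data were summarised. Against that, the only hint of 16 is the sum of two unlabelled counts.

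The argument about refusers is a separate matter and would exist had no sex counts been printed. Refusers are offered the other group and can still be followed up. Being left out of the statistical analysis does not by itself remove them from a retention count. Writing down that denominator would record a definition an analyst has to choose anyway. It would not correct line 10.

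**Conclusion.** Line 10 contains a clerical slip: sex counts totalling 16 beside a stated forty, a gap of 24, in a bracket that is otherwise unfilled. The counts are probably leftover or interim entries. That is an inference from the blank fields and the mixed tenses, not something the document states.

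Forty conflicts with no other design figure and supports no power statement, and no criterion or analysis uses the split. Labelling or deleting the counts, and saying what forty represents, would make the text cleaner, but recruitment, allocation, follow-up, analysis and conclusions would stay the same. The figures for a study of 16 describe a scenario the document does not support and should carry no weight. No change to the plan is called for.

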#### 88 *Data analysis*

89 All scores are standard derived from the tests itself, and data analyses processes have been published  
90 previously. Standard Operating Procedures are available upon request.

91 Statistical Analysis

92 Evaluation of the pilot consisted of the number of participants refusing to be allocated to their original  
93 group. If refused, participants were offered the alternative group ('cross-over'), but excluded from  
94 statistical analysis. Intervention recruitment, adherence (online platform usage, self-monitoring  
95 frequency, usage of support materials provided) and retention were considered sufficient if:

- 96 - with 3 participants per week (and relative to those screened, the consent rate taken into  
97 account),  
98 - adherence to the intervention program exceeding 70% and  
99 - 95% retained at follow up, respectively.

100 The lifestyle recommendations made were recorded for subsequent qualitative analyses and  
101 quantification of type of exercises included (balance, strength, flexibility, multi-component,  
102 equipment used, nutrition, physical activity tasks) as part of the pilot study evaluation.

103 Adverse event occurrence will be recorded. Protocol evaluation will consider time needed for the  
104 assessment and questionnaires and the consultation, support time needed for online monitoring and  
105 engagement during the intervention, to enable appropriate costing for future trials and revise  
106 accordingly. Participant characteristics (frailty, disability) will be summarized to determine future  
107 recruitment criteria.

108 Estimated sample size and confidence intervals will be initially based on primary outcome measures:  
109 Well-being (WEMWBS), Grip strength, Walking speed and SPPB. From those, but possible the  
110 secondary outcome measures, a primary outcome variable would be determined for the future  
111 randomized control trial.

112 Secondary outcome measures consist of:

- 113 - Functional ability performance, including timed-up-and-go, chair-stand test, balance,  
114 flexibility, 6MWT.  
115 - Dietary analyses  
116 - Healthcare Resource Use (i.e. hospital visits, GP appointments) assessed using a Healthcare  
117 Resource Use questionnaire at baseline and 12 weeks, to assess potential follow up impact  
118 due to inadvertent worrying of participants.  
119 - Qualitative feedback from assessors and participants about FACET  
120 Quality of life derived from the Short Form 36 item health questionnaire (SF36) at baseline  
121 and 12 weeks, including the Physical Component Summary (PCS)

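### Participants who refuse their allocated group are dropped from the analysis with nothing to offset this: planning figures describe accepters only, and any arm contrast could be modestly biased (cheap improvement, low severity)

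*Combined protocol and SAP*

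**What the plan says.** Under Procedures, the trial is a two-by-two factorial: "Arms were based on the factors of 'consultation type' and 'intervention support' and consisted of" four combinations. Participants are randomly allocated to a "group based on minimization for frailty status, age and gender".

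Under Statistical Analysis (lines 92–94), refusals are counted as a pilot result: "Evaluation of the pilot consisted of the number of participants refusing to be allocated to their original" group. The rule for refusers follows: "If refused, participants were offered the alternative group ('cross-over'), but excluded from". The sentence ends on the next line with the words statistical analysis, and no outcome or analysis set is exempted.

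Lines 108–111 say how the outcome data will be used: "Estimated sample size and confidence intervals will be initially based on primary outcome measures", namely "Well-being (WEMWBS), Grip strength, Walking speed and SPPB. From those, but possible the" secondary outcomes, one variable is to be chosen as primary for the future trial.

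The document gives no as-allocated analysis, no sensitivity analysis, no description of refusers by arm and no expected refusal rate. It names no between-arm contrast, and it does not say whether follow-up, change or baseline-adjusted scores will be used.

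**The concern.** Refusal happens after allocation and can depend on the arm offered. Two arms include an online platform with a diary and self-assessment, while the other two give recommendations on paper, so different people could refuse in different arms. The documents do not say that this happens.

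Two things are at stake:

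- **Planning figures.** Means, SDs and intervals describe accepters only. If the future trial analyses everyone it randomises, an SD from accepters may be too small.
- **Arm contrasts, if reported.** Removing refusers breaks the comparison of randomised groups when refusal is related to outcome and differs between arms in rate or type. Both conditions are needed.

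A count of refusals makes the exclusion visible but does not bring refusers' outcomes into the analysis.

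**Working it through.** The plan gives no figure to reproduce, so this is an illustration.

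**Inputs**

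- From the plan: "Forty older adults" (Participants, line 10) and the factorial design.
- Assumed: equal split, so 40/2 = 20 per factor level; refusal fraction q; refusers scoring d SD worse than accepters at follow-up; the same within-group SD (set to 1) in refusers and accepters.

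**1. Contrast bias, unadjusted follow-up scores.** Excluding refusers moves a level's mean by q × d, so bias = qA × dA − qB × dB. After exclusion, SE = √(1/nA + 1/nB). Coverage of a nominal 95% interval is Φ(1.96 − b/SE) − Φ(−1.96 − b/SE), with the SD taken as known.

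| Refusal in one level only | Bias (SD) | n | SE | Bias/SE | Coverage |
|---|---|---|---|---|---|
| q = 0.1, d = 0.5 | 0.05 | 18 v 20 | 0.325 | 0.15 | 94.7% |
| q = 0.2, d = 0.8 | 0.16 | 16 v 20 | 0.335 | 0.48 | 92.4% |
| q = 0.3, d = 0.8 | 0.24 | 14 v 20 | 0.348 | 0.69 | 89.4% |

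With 20% refusal in both levels and d = 0.8 in each, the bias is 0.16 − 0.16 = 0. Refusal unrelated to outcome (d = 0) also gives 0. Simulation with 100,000 runs agreed with the formula within 0.002.

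**2. SD of unadjusted follow-up scores, equal refusal in both levels.** Let v = q(1 − q)d². The all-randomised SD is √(1 + v) times the accepters' SD.

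- v = 0.0225, 0.1024 and 0.1344 for the three (q, d) pairs above.
- Ratio = 1.011, 1.050 and 1.065, so the accepters' SD is 1.1%, 4.8% and 6.1% too small.
- Sample-size shortfall 1 − 1/(1 + v) = 2.2%, 9.3% and 11.8%.
- If only one level has refusals, averaging the variance over levels (v/2) gives shortfalls of 1.1%, 4.9% and 6.3%.

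For scale, an SD on 30 degrees of freedom (32 analysed) has 95% limits of about 0.80 to 1.34 times the estimate.

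**3. Using the baseline value.** Suppose refusers differ by the same d at both visits, with within-group correlation ρ (assumed; the documents give none).

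- Change scores: contrast bias and SD shortfall are both about 0.
- Baseline adjustment: bias = q × d × (1 − ρ). For q = 0.2, d = 0.8, ρ = 0.7: 0.16 × 0.3 = 0.048 SD. For ρ = 0.5 and 0.9: 0.08 and 0.016 SD.
- Adjustment also shrinks the SE by about √(1 − ρ²). At ρ = 0.7 it is 0.335 × 0.714 = 0.239, so bias/SE falls from 0.48 to 0.20.
- The residual variance in all randomised is (1 + v) − (ρ + v)²/(1 + v). At ρ = 0.7 this is 1.1024 − 0.8024²/1.1024 = 0.518, against 1 − 0.49 = 0.51 in accepters. The shortfall is 1 − 0.51/0.518 = 1.6%, compared with 9.3% unadjusted. For ρ = 0.5 and 0.9 it is 3.0% and 0.5%.

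**4. Sample size.** Line 10 states forty participants but gives 6 female and 10 male, which total 16. At 8 v 8 the SE before any exclusion is √(2/8) = 0.50 SD, so the largest one-sided bias is 0.24/0.50 = 0.48 of a standard error.

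**The case against.** The strongest reply is that this is a pilot. It names no between-arm estimate or test, so the contrast bias attaches to an analysis the plan does not state. That stands, and it is why the claim about contrasts is conditional. The accepters-only point needs no contrast, but its effect on the SD matters only if the future trial analyses refusers. If that trial excludes them too, the accepters' SD is the relevant one.

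It is also fair to say that everything about refusal is assumed. With no refusals the issue disappears, and participants were told the nature of the study before consenting, which may keep refusal low. Every illustrated bias is below one standard error. Baseline measurements are planned at visits 1 and 2, so adjustment is feasible. It would not help if refusers diverge only after baseline.

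Finally, an as-allocated analysis answers a different question and is diluted by cross-over. That is a real cost, set out under the fix.

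A reader might go further and infer that the arm comparisons are invalid, or that the future trial will be about 10% too small. The documents support neither. The first needs a reported contrast and refusal that is both outcome-related and different between arms. The second needs substantial refusal, unadjusted follow-up scores and a future trial that analyses refusers.

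**Conclusion.** The point holds in a limited form. It is certain that the plan excludes refusers after randomisation and that nothing offsets this. It follows that, if anyone refuses, the planning estimates describe accepters only. The numerical effect is unknown. Under the assumptions shown (20 v 20, unadjusted follow-up scores), a reported contrast would be biased by 0.05–0.24 SD for one-sided refusal of 10–30%, and the SD would be 1–6% too small for equal refusal at those rates. With change scores or baseline adjustment, and refusers differing equally at both visits, the middle case falls from 0.16 SD to about 0 or 0.05 SD, and the 9% sample-size shortfall falls to 0–2% at a correlation of 0.7. With fewer participants than forty, the bias is smaller still relative to the standard error. This is a cheap improvement of low severity.

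**What to change.** Replace the exclusion with wording such as:

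> All randomised participants with follow-up data are analysed in the arm to which minimisation allocated them, adjusting for the baseline value of the outcome. Those who refuse or cross over are invited to visit 3. Refusals and missing visit 3 data are reported by allocated arm with baseline characteristics. An analysis excluding cross-overs is a sensitivity analysis.

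The offer of the alternative group is unchanged. The cost is SAP wording plus an invitation to a visit that already exists; the documents do not say whether refusers attend it.

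There are two downsides:

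- **Dilution.** The main estimate becomes the effect of allocation. If 10%, 20% or 30% of one level cross over fully on the factor contrasted, it is 1 − q = 0.9, 0.8 or 0.7 of the full effect. The actual amount cannot be settled, because the plan does not define which of the other three arms is the alternative. Only if the future sample size used the pilot's observed effect would this multiply it, by 1/(1 − q)² = 1.2, 1.6 or 2.0.
- **Incomplete recovery.** Refusers who do not attend visit 3 remain outside the analysis, so selective attendance could leave part of the bias. Reporting missing visit 3 data by arm would show how far this applies.

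### Does leaving open how the future trial's primary outcome and target difference will be chosen make that trial underpowered?

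*Combined protocol and SAP*

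**What the plan says.** Under Statistical Analysis, line 108 opens with "Estimated sample size and confidence intervals will be initially based on primary outcome measures". Lines 109-111 name the measures and continue: "Well-being (WEMWBS), Grip strength, Walking speed and SPPB. From those, but possible the" and then "secondary outcome measures, a primary outcome variable would be determined for the future" randomised trial. The candidate pool may therefore extend to the secondary list, which begins with "Functional ability performance, including timed-up-and-go, chair-stand test, balance" and runs on to flexibility, the 6MWT, diet, healthcare resource use and the SF-36. That list also includes "Qualitative feedback from assessors and participants about FACET".

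The documents give no target or minimal important difference, SD, alpha or power for the future trial, and no rule for choosing its primary outcome. The numerical success criteria (lines 96-99) cover recruitment, adherence and retention only, the last being "95% retained at follow up, respectively". On design, Procedures states: "The trial used a parallel-group design with four intervention arms in a two-by-two factorial design".

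**The concern.** A pilot of about 40 people estimates effects very imprecisely. If a team looks at several outcomes, keeps the one with the largest between-arm difference and sizes the next trial on that difference, the estimate is biased upwards and the next trial is too small. Lines 108-111 make the outcome choice and the sample size outputs of this pilot, and contain nothing that excludes that use. The plan sets thresholds for its feasibility outputs, so the lack of any rule for the two statistical outputs stands out. At stake is a future trial that could miss a worthwhile effect.

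**Working it through.** The plan has no sample-size figure to reproduce, so the check compares what the future trial would look like under different readings of lines 108-111.

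**Inputs from the documents.** Four candidate outcomes (line 109); a 2x2 factorial with four arms (Procedures); forty participants (Participants). The sex counts in the same sentence add to 6 + 10 = 16, beside unfilled placeholders; forty is used here.

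**Assumptions, because the documents give none.** Two-sided 5%, planned power 80%, equal allocation, comparison on one factor's margin (20 vs 20), true standardised effect d of 0.2, 0.3 or 0.5, a common correlation between outcomes, and equal true effects unless stated.

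**Precision of the pilot.** SE of a standardised difference = sqrt(2/20) = 0.316, so the 95% half-width is 1.96 x 0.316 = 0.62.

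**Size needed.** n per group = 2(1.96 + 0.842)^2/d^2. At d = 0.3 this is 2 x 7.85/0.09 = 174.4, so 175. At d = 0.2 and 0.5 it is 393 and 63.

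**Reading 1: the pilot supplies only the SD, and the target difference is fixed from outside.** The SD estimate has 34 df (38 analysed, four arms) and s^2 follows chi-square(34)/34. At d = 0.3 the median planned size is 172 per group. Power is Phi(0.3 x sqrt(172/2) - 1.96) = Phi(0.82) = 79%. The median is also 79% at d = 0.2 and 0.5. Imprecision in the SD remains: 53% of such trials have under 80% power. In a run with the SD taken from a 20 vs 20 pilot, the 5th to 95th percentiles of power were 62% to 91%.

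**Reading 2: one prespecified outcome, sized on its observed effect.** The observed effect is centred on the true one, so with every pilot kept the median planned size at d = 0.3 is about 175 and median power is 80%, with half of trials below. A lower median appears only if pilots with small observed effects are assumed to be abandoned. At d = 0.3 it is 63%, 59%, 54% or 46% when the cut-off on observed d is 0, 0.05, 0.1 or 0.2. That figure depends on a go/no-go rule that the plan does not contain.

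**Reading 3: the largest of four observed effects is chosen and the trial sized on it.** Simulation with 200,000 pilots per scenario, dropping those whose largest observed d is 0.05 or less (2% at d = 0.3, correlation 0.3):

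| Common correlation | Median power, d = 0.2 | d = 0.3 | d = 0.5 |
|---|---|---|---|
| 0 | 19% | 28% | 41% |
| 0.3 | 21% | 31% | 45% |
| 0.5 | 23% | 34% | 49% |

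At d = 0.3 and correlation 0.3 the largest observed effect averages 0.57 and the median planned size is 48 per group against 175 needed. Check: Phi(0.3 x sqrt(48/2) - 1.96) = Phi(-0.49) = 31%.

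The range 0 to 0.5 does not bound the uncertainty, because usual walking speed is a component of the SPPB (lines 59-62) and two of the four candidates overlap by construction. At a common correlation of 0.8 the median at d = 0.3 is 42%. Unequal true effects of 0.1, 0.2, 0.3 and 0.4 give 35%. With 16 participants (8 vs 8) it is 21% at d = 0.3.

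The large loss therefore comes from selection on observed effects combined with sizing on them. Neither step is written in the plan.

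**The case for a change.** The strongest case for a change is that the wording permits the harmful reading and a few words would close it off. The choice was still to be made, the participant and assessor feedback needed for a choice blind to between-arm results is already collected, and the secondary list makes the pool larger than four. Under the harmful reading the loss is large: at d = 0.3 and correlation 0.3, 87.5% of future trials with a usable effect would have under 80% power. All of that stands as arithmetic.

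It does not show that the plan prescribes anything wrong. The text says neither that the largest effect will be chosen nor that the pilot effect will be used for sizing. Line 108 calls the sizing initial and pairs it with confidence intervals; with a half-width of about 0.62, those intervals would show plainly how little the pilot says about effects. Even under the harmful reading, underpowering is likely rather than certain: with equal true effects about 5% to 20% of simulated trials still reached 80% power, and up to 46% did when one outcome truly dominated. An upper confidence limit for the SD is one convention among several and deals with SD imprecision, which is a different matter from outcome selection.

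**Conclusion.** The omission is real, but it is missing detail and not an error in a stated method. A competent team would ordinarily fill it by choosing the outcome on relevance, completeness and measurement properties, taking the target difference from outside the pilot, and using the pilot for the SD, the baseline-to-follow-up correlation and attrition. On that reading median power is about 79%. Only if the outcome and the effect size were both taken from the largest observed difference would median power fall to about 28% to 42% (assumed true d = 0.3, 20 vs 20, four candidates, correlations 0 to 0.8).

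The future trial's protocol must justify its own primary outcome and sample size, and that is where such a misuse would be caught. Nothing in this pilot's conduct, participant safety or own results depends on the point. A sentence stating the intended use of the pilot data would be a courtesy to readers; the plan does not need it.
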